8.2 Nivolumab

Refer to the current package insert for nivolumab contraindications and adverse reactions.

8.3 Adverse Event Reporting Requirements

Adverse event (AE) monitoring and reporting is a routine part of every clinical trial and is done to ensure the safety of subjects enrolled in the studies as well as those who will enroll in future studies using similar agents. Data on adverse events will be collected from the time of the initial study treatment administration through 60 days after the last dose of study treatment.

In addition to new events, any increase in the frequency or severity (i.e., toxicity grade) of a pre-existing condition that occurs after the patient begins study treatment is also considered an adverse event.

8.4 Definitions

8.4.1 Adverse Event

An adverse event (AE) is any untoward medical occurrence in a patient receiving study treatment and which does not necessarily have a causal relationship with this treatment. An AE can be any unfavorable and unintended sign (including an abnormal laboratory finding), symptom, or disease temporally associated with the use of an experimental intervention, whether or not related to the intervention.

- *Diagnostic and therapeutic non-invasive and invasive (i.e., surgical) procedures will not be reported as adverse events. However, the medical condition for which the procedure was performed must be reported if it meets the definition of an adverse event unless it is a pre-existing (prior to protocol treatment) condition.*
- *Abnormal laboratory values or test results constitute adverse events if they induce clinical signs or symptoms or require therapy. They are to be captured under the signs, symptoms or diagnoses associated with them.*

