2.5 Secondary Endpoints

2.5.1 To assess the objective response rate (complete response and partial response) by RECIST 1.1 in metastatic renal cell cancer to ESK981 monotherapy.

2.5.2 To determine frequency and severity of adverse events by CTCAE criteria of ESK981 in patients with metastatic renal cell carcinoma.

2.5.3 To evaluate secondary efficacy measures such as overall survival, progression free survival, duration of therapy, duration of response to ESK981 monotherapy in Cohort A and to the combination in Cohort B; response by combined RECIST v1.1 and irRECIST and irRECIST progression free survival (Cohort B only).

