5.2 Toxicities and Dosing Delays/Dose Modifications

Any patient who receives treatment on this protocol will be evaluable for toxicity. Each patient will be assessed for the development of toxicity according to the Time and Events Table (Section 6.1). Toxicity will be assessed according to the NCI Common Terminology Criteria for Adverse Events (CTCAE), version 4.03. Dose adjustments should be made according to the system showing the greatest degree of toxicity.

Table 5.2.1 Hematological Toxicities

Hematological Toxicity Dose Reductions for ESK981		
ANC ¹	Platelets	Action
≥ 1,500/ μ L or	>100,000/μL	None.
1000-1499/ μ L or	75,000-99,000/μL	
-1st Occurrence: Hold current dose until ANC ≥ 1,500/μL and platelets ≥ 100,000/μL. Do not replace missed doses. Restart next treatment at 1 dose lower.
 
-2nd Occurrence: Hold current dose until ANC ≥ 1,500/μL and platelets ≥ 100,000/μL. Do not replace missed doses. Restart next treatment at 1 dose lower if available or discontinue if not available
 
-3rd Occurrence: Discontinue protocol therapy.

500-999/ μ L or	50,000-74,000/μL	
-1st Occurrence: Hold current dose until ANC ≥ 1,500/μL and platelets ≥ 100,000/μL. Do not replace missed doses. Restart next treatment at 1 dose lower if available or discontinue if not available.
 
-2nd Occurrence: Hold current dose until ANC ≥ 1,500/μL and platelets ≥ 100,000/μL. Do not replace missed doses. Restart next treatment at 1 dose lower if available or discontinue if not available.
 
-3rd Occurrence: Discontinue protocol therapy.

<500/ μ L or	<50,000/μL	
-1st Occurrence: Hold current dose until ANC ≥ 1,500/μL and platelets ≥ 100,000/μL. Restart next treatment at 1 dose lower if available or discontinue if not available.
 
-2nd Occurrence: Discontinue protocol therapy.

¹Note: G-CSF (Filgrastim) may be added for low ANC on day of treatment *BEFORE* a dose reduction is instituted at treating physician's discretion. Neulasta® is NOT allowed.

Treatment-Emergent Non-hematological Toxicities: (EXCEPT non-clinically relevant/significant laboratory abnormalities):

NCI CTCAE Grade	ESK981	Nivolumab
1	No change from original starting dose	No change from original starting dose, supportive care as required
2	Hold until resolved to ≤ Grade 1, then reduce by 1 dose level if available or discontinue if not available	Hold until resolved to ≤ Grade 1, supportive care as required and then resume treatment

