7.2 Safety/Tolerability

Analyses will be performed for all patients having received at least one dose of study drug. The study will use the CTCAE version 4.03 for reporting of non-hematologic adverse events (https://www.eortc.be/services/doc/ctc/CTCAE_4.03_2010-06-14_QuickReference_5x7.pdf) and modified criteria for hematologic adverse events.

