8.5 Adverse Event Characteristics

8.5.1 CTCAE Term

(AE description) and grade: The descriptions and grading scales found in the NCI Common Terminology Criteria for Adverse Events (CTCAE) version 4.03 will be utilized for AE reporting. All appropriate treatment areas should have access to a copy of the CTCAE version 4.03. A copy of the CTCAE version 4.03 can be downloaded from the CTEP web site. (https://www.eortc.be/services/doc/ctc/CTCAE_4.03_2010-06-14_QuickReference_5x7.pdf

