11.4 Data Analyses Plans

The primary analysis of efficacy will report the number of patients with an objective response and the associated proportion with the corresponding 95% exact binomial confidence interval separately in each cohort. In Cohort B, if stage 2 is initiated then the efficacy analysis methods will be adjusted for the interim check as described by Koyama and Chen [36].

Toxicity will be described by grade, attribution, and body system using counts and proportions. Toxicity will be described separately for each cohort.

Overall survival, progression free survival, duration of therapy, and duration of response will be displayed using a Kaplan-Meier figure and the associated median (if reached), one-year and two-year estimates with 95% confidence intervals using Greenwood's formula will be reported if there is censoring. If there is no censoring in the endpoint, then the standard mean (or median) and 95% confidence interval (or 5th and 95th percentiles) will be reported. Each endpoint will be reported separately by cohort.

Health-related quality of life assessment changes from baseline using EuroQoL-5D will be described using descriptive statistics.

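### Hematologic toxicity has no settled grading scale or recording rule, so asymptomatic cytopenias may be missing from the adverse event endpoint

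*Combined protocol and SAP*

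**What the plan says.** **Endpoint and analysis.** Secondary endpoint 2.5.2 reads "To determine frequency and severity of adverse events by CTCAE criteria of ESK981". Section 11.4 plans one safety summary: "Toxicity will be described by grade, attribution, and body system using counts and proportions", separately by cohort. It names no summary of laboratory grades.

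**Grading scale.** Section 5.2 says "Toxicity will be assessed according to the NCI Common Terminology Criteria for Adverse Events (CTCAE), version 4.03". Section 8.5.1 says of CTCAE that "version 4.03 will be utilized for AE reporting". Neither makes an exception for hematologic events. Section 7.2 limits CTCAE 4.03 to non-hematologic events and assigns the rest to "modified criteria for hematologic adverse events". No section says what the modification is.

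**What counts as an adverse event.** Section 8.4.1 opens broadly: "An AE can be any unfavorable and unintended sign (including an abnormal laboratory finding), symptom, or disease temporally associated" with the intervention. A bullet below it is narrower: "Abnormal laboratory values or test results constitute adverse events if they induce clinical signs or symptoms or require therapy". It adds: "They are to be captured under the signs, symptoms or diagnoses associated with them".

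**What else depends on laboratory values.** Table 5.2.1 holds, reduces or stops ESK981 on neutrophil or platelet counts, with no requirement for symptoms. The Time and Events Table (Section 6.1) collects a blood count with differential weekly in Cycles 1 and 2, and a metabolic panel each cycle.

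**The concern.** Frequency and severity of adverse events is a secondary endpoint, and both parts depend on rules that the plan leaves open. Severity needs a grading scale, and for hematologic events the plan gives two, one of them undefined. Frequency needs a rule for what is recorded, and 8.4.1 gives two statements that lead to different records for the same blood count. The synopsis names two sites, which could apply them differently.

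At stake is whether the safety tables agree with the dosing records. A patient could have ESK981 held, reduced or stopped for a low count and yet have no hematologic adverse event on file. The laboratory data to prevent this are collected, but 11.4 does not say they will be summarised.

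**Working it through.** **1. Grading scale, provisions side by side.**

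| Section | Scale for hematologic events |
|---|---|
| 2.5.2 | CTCAE, no version given |
| 5.1 (DLT definition) | CTCAE 4.03 |
| 5.2 | CTCAE 4.03 |
| 8.5.1 | CTCAE 4.03 |
| 7.2 | Modified criteria, undefined |

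Section 7.2 cannot be reconciled with the others as written. Because the modification is unknown, so is its direction: it could raise or lower grades.

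**2. Recording rule, applied to one case.** Take a neutrophil count of 1000-1499/µL in a patient with no symptoms and no therapy.
- Table 5.2.1: ESK981 is held and the dose changed. A third occurrence ends protocol therapy.
- Section 8.4.1, general definition: can be an adverse event.
- Section 8.4.1, laboratory bullet: does not meet the stated condition.

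If the bullet governs, the count appears in the dosing record and not among the adverse events. If G-CSF is given, as the footnote to Table 5.2.1 allows, the therapy condition is met and the event qualifies. Lymphopenia has no column in Table 5.2.1, so an asymptomatic case need not appear in the dosing record either.

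**3. Phase 1 context (Section 1.2.4).**
- Grade 3-4 laboratory hematologic toxicity: 8/43 = 18.6%, which matches the stated figure. The exact 95% confidence interval is 8.4% to 33.4%.
- Grade 3-4 lymphopenia is reported in 8 patients, so all 8 had it.
- Grade 3-4 neutropenia: 2 patients at 97.4 mg/m² and 1 at 126.6 mg/m², so 3/43 = 7.0%. If these three are among the eight, 8 - 3 = 5 had lymphopenia without Grade 3-4 neutropenia.

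**4. How much could be missed.** Let p be the true proportion of patients with such an abnormality and f the share of them who are asymptomatic and untreated. If the bullet governs, the proportion reported as adverse events is p × (1 - f). The documents do not give f, so the full range is shown at the phase 1 rates.

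| f (assumed) | Any Grade 3-4 hematologic, p = 18.6% | Grade 3-4 neutropenia, p = 7.0% |
|---|---|---|
| 0 | 18.6% | 7.0% |
| 0.25 | 14.0% | 5.2% |
| 0.50 | 9.3% | 3.5% |
| 0.75 | 4.7% | 1.7% |
| 1 | 0% | 0% |

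The neutropenia column is closer to the dosing mismatch in step 2. The first column is driven by lymphopenia. Neither gives the frequency of the count bands in Table 5.2.1, which the documents do not report for phase 1.

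**The case against.** **The laboratory bullet says if, not only if.** A reader might infer that 8.4.1 firmly excludes asymptomatic laboratory findings. The text does not go that far, because the general definition above it includes them. This part stands: the defect is an internal inconsistency. It does not remove the problem, since the bullet would have no function if every abnormal value already counted.

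**Section 11.4 speaks of toxicity, not adverse events.** The protocol uses that word for count-based findings in Table 5.2.1 and in footnote 13 of the Time and Events Table. Graded cytopenias could therefore fall within 11.4 whatever 8.4.1 says. That reading is available, so omission is possible and not proven. Against it, 11.4 breaks toxicity down by attribution, which Section 8.5.2 assigns to adverse events, and endpoint 2.5.2 names adverse events.

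**A reader might infer that safety will be understated.** The documents do not support a certain downward bias. The undefined criteria could move grades either way, and treated cytopenias still qualify. Only the laboratory bullet has a fixed direction: it can lower counts and cannot raise them.

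**A reader might infer that about 9 of the 47 patients will be missing (0.186 × 47 = 8.7).** That is not supported either. The 47 is the response-evaluable count in Section 11.2. The safety population is everyone dosed (Sections 7.1.1 and 7.2), and non-evaluable patients are replaced (Section 5.7). The 18.6% pools daily dosing from 3.0 to 126.6 mg/m², whereas this trial gives a flat 160 mg five days a week. All eight patients behind it had lymphopenia, which triggers nothing in Table 5.2.1.

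**The toxicity stopping rules are separate.** DLTs have their own laboratory exception in Section 5.1, based on clinical relevance, so Section 11.3 does not depend on 8.4.1. This stands in full.

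**Conclusion.** Two defects hold on the text alone. Section 7.2 conflicts with 5.2, 8.5.1 and 2.5.2 and leaves the hematologic severity scale undefined, and 8.4.1 contradicts itself on laboratory findings. A third point is conditional. If the laboratory bullet governs and 11.4 draws on adverse event records, asymptomatic untreated cytopenias may be missing from the safety endpoint. That would include counts that lead to an ESK981 hold, reduction or discontinuation.

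The size of any under-reporting is unknown. At the phase 1 rates it lies between none and the full 18.6% of patients for any Grade 3-4 hematologic laboratory toxicity, or the full 7.0% for neutropenia. Both ranges assume that those rates carry over to a different dose and schedule. The primary endpoint, sample size, type I error, power and dosing rules are unaffected. The change is worth making because it concerns the hematologic laboratory toxicity that phase 1 documented and the data are already collected.

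**What to change.** 1. **Section 11.4.** Add a table by cohort, in all treated patients, of the worst post-baseline CTCAE 4.03 grade for each blood count and chemistry analyte. Derive it from laboratory values, independently of adverse event reporting. This is the essential step, because it captures lymphopenia whether or not dosing changed.
2. **Section 7.2.** Remove the hematologic exception so that grading matches 5.2, 8.5.1 and 2.5.2. If modified criteria were intended, define them and report CTCAE 4.03 grades alongside.
3. **Section 8.4.1.** Reconcile the general definition with the laboratory bullet. Also record as adverse events those laboratory abnormalities that lead to a hold, reduction or discontinuation. On its own this step would still miss lymphopenia that changes no dosing.

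The cost is protocol wording and one table from data already collected. The downside is a few more adverse event records and a less favourable-looking safety table.

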8.4.2 Serious Adverse Event

An adverse event is considered “serious” if, in the view of either the investigator, it results in any of the following outcomes:

- Death
If death results from (progression of) the disease, the disease should be reported as event (SAE) itself.
- A life-threatening adverse event
An adverse even is considered ‘life-threatening’ if, in the view of either the investigator [or sponsor], its occurrence places the patient or subject at immediate risk of death. It

does not include an adverse event that, had it occurred in a more severe form, might have caused death.

- Inpatient hospitalization or prolongation of existing hospitalization for \geq 24 hours.
- A persistent or significant incapacity or substantial disruption of the ability to conduct normal life functions
- A congenital anomaly/birth defect
- Important medical event
Any event that may not result in death, be life-threatening, or require hospitalization may be considered serious when, based upon appropriate medical judgment, they may jeopardize the patient and may require medical or surgical intervention to prevent one of the outcomes listed in this definition of "Serious Adverse Event". Examples of such medical events include allergic bronchospasm requiring intensive treatment in an emergency room or at home; convulsions that do not result in inpatient hospitalization or the development of drug dependency or drug abuse.

Previously planned (prior to signing the informed consent form) surgeries should not be reported as SAEs unless the underlying medical condition has worsened during the course of the study. Preplanned hospitalizations or procedures for preexisting conditions that are already recorded in the patient's medical history at the time of study enrollment should not be considered SAEs. Hospitalization or prolongation of hospitalization without a precipitating clinical AE (for example, for the administration of study therapy or other protocol-required procedure) should not be considered SAEs. However, if the preexisting condition worsened during the course of the study, it should be reported as an SAE.

8.4.3 Expected Adverse Events

An adverse event (AE) is considered "expected" if:

- For approved and marketed drugs or devices, those adverse events are described in the approved Package Insert (Label).
- For investigational new drugs or devices, those adverse events are described in the FDA Investigator's Brochure.
- In clinical research studies, information on expected adverse events is also summarized in the protocol and in the consent document.

8.4.4 Unexpected Adverse Event

An adverse event (AE) is considered "unexpected" if it is not described in the Package Insert, Investigator's Brochure, in published medical literature, in the protocol, or in the informed consent document.

8.5 Adverse Event Characteristics

8.5.1 CTCAE Term

(AE description) and grade: The descriptions and grading scales found in the NCI Common Terminology Criteria for Adverse Events (CTCAE) version 4.03 will be utilized for AE reporting. All appropriate treatment areas should have access to a copy of the CTCAE version 4.03. A copy of the CTCAE version 4.03 can be downloaded from the CTEP web site. (https://www.eortc.be/services/doc/ctc/CTCAE_4.03_2010-06-14_QuickReference_5x7.pdf

8.5.2 Attribution of the AE

The investigator or co-investigator is responsible for assignment of attribution.

Definite – The AE is *clearly related* to the study treatment.

Probable – The AE is *likely related* to the study treatment.

Possible – The AE *may be related* to the study treatment.

Unlikely – The AE is *doubtfully related* to the study treatment.

Unrelated – The AE is *clearly NOT related* to the study treatment.

8.6 Serious Adverse Event Reporting Guidelines

All serious adverse events (SAEs) and unanticipated problems (UPs), regardless of causality to study drug, will be reported to the Principal Investigator and also to the Coordinating Center. All SAEs and UPs must be reported to the Coordinating Center within 24 hours of first awareness of the event. Events should be reported using the Coordinating Center SAE form as available in the study database. A copy of the Coordinating Center SAE form as available in the study database should be sent to the Coordinating Center via fax at [contact] or via email to [contact] within 24 hours of the site's knowledge of the event.

Follow-up information should also be reported within 24 hours of receipt of the information by the investigator.

All SAEs and UPs will be reported to the IRB per current institutional standards.

The Coordinating Center will disseminate information regarding SAEs and UPs to the participating sites within 5 days of review of the information by the Coordinating Center's Principal Investigator (or designee in the event of extended absence) only in the case that the event(s) is believed to be related (i.e., possibly, probably, or definitely) to the study drug. The Coordinating Center will be responsible for reporting of events to the FDA and supporters, as appropriate (outlined below).

8.6.1 Reporting procedures to Esanik

All Serious Adverse Events (SAEs) occurring from the initial study treatment administration through 60 days following the last dose of the study treatment will be reported by the Coordinating Center to Esanik. Any SAEs occurring after 60 days following the last dose of the study treatment that are believed to be related to study drug will also be reported to Esanik.

The Coordinating Center will send the initial completed SAE Form within 24 hours of receipt via email to Esanik:

Email: [contact]. The Coordinating Center will confirm receipt of the email by calling [contact]

If only limited information is initially available or an ongoing SAE changes in its intensity or relationship to the study drug, or if new information becomes available, a follow-up report will be generated and sent to Esanik within 24 hours of receipt.

8.6.2 Reporting procedures to the FDA

In this trial, serious unexpected adverse events believed to be definitely, probably or possibly related to the study treatment will be reported to the Food and Drug Administration via the MedWatch 3500A. The Michigan IND/IDE Assistance Program (MIAP) (University of Michigan) will assist the IND Sponsor in reporting SAEs to the FDA that meet the reporting

requirements in 21 CFR 312.32. This reporting could include the initial report and follow-up reports when appropriate for the event.

All correspondence to the FDA by sponsor-investigator should be provided to Esanik.

8.7 Routine Reporting

All other adverse events- such as those that are expected, or are unlikely or definitely not related to the study participation- are to be reported annually as part of regular data submission.

8.8 Reporting of Unanticipated Problems

There are types of incidents, experiences and outcomes that occur during the conduct of human subjects research that represent unanticipated problems but are not considered adverse events. For example, some unanticipated problems involve social or economic harm instead of the physical or psychological harm associated with adverse events. In other cases, unanticipated problems place subjects or others at increased risk of harm, but no harm occurs.

Upon becoming aware of any incident, experience, or outcome (not related to an adverse event) that may represent an unanticipated problem, the investigator should assess whether the incident, experience, or outcome represents an unanticipated problem. The incident, experience or outcomes is considered unanticipated if it meets all of the following criteria:

1. Unexpected (in terms of nature, severity, or frequency);
2. Related or possibly related to participation in the research; and
3. Suggests that the research places subjects or others at a greater risk of harm than was previously known or recognized.

If the investigator determines that the incident, experience, or outcome represents an unanticipated problem, the investigator must report it to the Coordinating Center within 2 calendar days of the study team becoming aware of the problem and report to their local IRB as per institutional guidelines.

